##### 4.4.1.1.2 Maximum Overall Intensity

Maximum overall intensity will be derived from the daily intensities computed as described in Section 4.4.1.1.1 and will be calculated as the maximum of the daily intensities during the period considered.

##### 4.4.1.1.3 Presence

Presence will be derived from the maximum overall intensity during the period considered:

None: No presence

Grade 1, Grade 2, or Grade 3: Presence

Missing: Missing presence

Subjects with at least 1 non-missing presence for a specific endpoint will be included in the analysis. Conversely, those with all missing presence will not be included in the analysis of the endpoint.

#### 4.4.1.1.4 Time to Onset

Time to onset will be derived from the daily intensities computed as described in Section 4.4.1.1.1. It will correspond to the first day with an intensity of Grade 1, Grade 2, or Grade 3.

Note: If a reaction is not continuous (i.e., reaction occurs during 2 separate periods of time intervened by at least 1 daily intensity of Missing or None) then the time to onset is the first day of the first occurrence. For subjects who received 2 doses, the worst-case scenario will be used for the post-any dose summary (i.e., the shorter time to onset [latency] period will be used if present for both doses, or the available time to onset [latency] period will be used if present for either dose).

#### 4.4.1.1.5 Number of Days of Occurrence

Number of days of occurrence during the period considered will be derived from the daily intensities computed as described in Section 4.4.1.1.1. It corresponds to the number of days with daily intensities of Grade 1, Grade 2, or Grade 3. The number of days of occurrence during the solicited period with a specified intensity may also be derived. For subjects who received 2 doses, the worst-case scenario will be used for the post-any dose summary (i.e., the larger number of days will be used if present for both doses, or the available number of days will be used if present for either dose).

#### 4.4.1.1.6 Overall Number of Days of Occurrence

If a reaction is ongoing at the end of the solicited period, then the overall number of days of occurrence will be derived from the daily intensities and the stop date of the reaction after the end of the solicited period. The overall number of days of occurrence will be:

$$(\text{stop date} - \text{last vaccination date}) + (\text{number of days of occurrence within the solicited period}) - \text{length of the solicited period} + 1$$

If the stop date is missing or incomplete (contains MD), the overall number of days of occurrence will be considered as Missing. For subjects who received 2 doses, the worst-case scenario will be used for the post-any dose summary (i.e., the larger number of days will be used if present for both doses, or the available number of days will be used if present for either dose).

#### 4.4.1.1.7 Ongoing

Ongoing will be derived from the last daily intensity of the solicited period computed as described in Section 4.4.1.1.1 and the maximum intensity during the ongoing period. The Investigator's ongoing flag is not used because the measurement would determine the ongoing status of the reaction.

If the last daily intensity of the solicited period is at least Grade 1 and the maximum intensity in the ongoing period is also at least Grade 1, then the reaction is considered ongoing. In all other cases, the reaction will not be considered as ongoing.

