## 4.4 Derived Endpoints: Calculation Methods

### 4.4.1 Safety

#### 4.4.1.1 Solicited Reactions

##### 4.4.1.1.1 Daily Intensity

All daily intensities will be derived from daily records for solicited reactions according to the following classification: None, Grade 1, Grade 2, Grade 3, or Missing.

For the derivation of daily intensities, the following sequential steps will be applied:

- 1) For solicited reactions (except fever/pyrexia) for which an Investigator records their presence as “No” and for which all daily records are missing, all daily intensities will be derived as None
- 2) For a temperature with partially missing data (MD) after the decimal point, the data will be analyzed by replacing “MD” with zero. For example, a “39.MD°C” daily temperature will be considered as “39.0°C” in the analysis
- 3) For non-measurable solicited reactions, daily intensities will correspond to daily records reported in the clinical database. For measurable solicited reactions, the daily measurements reported in the clinical database will be converted based upon the intensity scales defined in the protocol; this assumes a reaction that is too large to measure (non-measurable, “NM”) is Grade 3

Note: The maximum intensity during the ongoing period will be derived from the record of the maximum intensity/measurement after the end of the solicited period following the rule described above.

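### A Missing intensity makes a solicited reaction not ongoing under SAP 4.4.1.1.7, so a recorded stop date after Day 7 is left out of the overall number of days

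*SAP*

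**What the plan says.** SAP 4.4.1.1.1 classifies daily intensities as "None, Grade 1, Grade 2, Grade 3, or Missing". It applies the same derivation to the period after Day 7, which has a single summary record: "The maximum intensity during the ongoing period will be derived from the record of the maximum intensity/measurement after the end of the solicited period".

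SAP 4.4.1.1.7 sets the investigator's own indication aside: "The Investigator's ongoing flag is not used because the measurement would determine the ongoing status of the reaction". Ongoing status requires at least Grade 1 on both the last daily intensity and the after-period maximum. For everything else the text is "In all other cases, the reaction will not be considered as ongoing".

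SAP 4.4.1.1.6 brings in the stop date under a condition: "If a reaction is ongoing at the end of the solicited period, then the overall number of days of occurrence will be derived", using the daily intensities together with the stop date. If that date is missing or incomplete, the overall number of days is Missing. SAP 5.3.1.5 says the same for a reaction that continues past the solicited period.

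SAP 4.4.1.1.5 separately defines a within-period number of days, which counts days graded 1 to 3 and does not depend on ongoing status. Protocol 9.3.1.3.2 has reactions recorded over Days 0-7 and until resolution, so later stop dates are expected in the data.

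**The concern.** The rule handles an unknown intensity as if the reaction were known to have ended. Two incomplete records of the same late reaction then get opposite treatment:

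- Intensities known, stop date missing: the overall number of days is Missing, and a reader can see that something is absent.
- Stop date known, one intensity missing: the count is short but looks complete, and the recorded date plays no part.

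SAP 5.3.1.3 and 5.3.1.4 otherwise leave missing measurements and qualifiers missing, so the second outcome is out of step with the plan's general approach. It also works in one direction only. Wherever a late stop date goes unused, the overall count is shortened, and this happens only to reactions that lasted past Day 7. For two-dose children, the shortened value can then enter the larger-of-two-doses summary in 4.4.1.1.6.

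**Working it through.** The plan states no duration figure to reproduce, so the check applies its rules literally.

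**Step 1: which records are ongoing.** Inputs: the intensity classes of SAP 4.4.1.1.1 and the rule of 4.4.1.1.7, taking the last daily intensity to be Day 7.

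| Day 7 intensity | Later maximum None | Later maximum Grade 1 or more | Later maximum Missing |
|---|---|---|---|
| None | not ongoing | not ongoing | not ongoing |
| Grade 1 or more | not ongoing | **ongoing** | not ongoing |
| Missing | not ongoing | not ongoing | not ongoing |

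One of the 9 cells is ongoing. All 5 cells with a Missing value are not ongoing, whatever the stop date or flag says. Two of those 5 also contain a recorded None, which is a fair reason for the result. The other 3 contain no evidence that the reaction ended.

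**Step 2: the day formula.** SAP 4.4.1.1.6 gives

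overall days = (stop date - last vaccination date) + days within the solicited period - length of the solicited period + 1.

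The length is taken as 8, since Day 0 to Day 7 is 8 daily records. With that value the formula agrees with a calendar count. For Grade 1 on Days 5, 6 and 7 and stop Day 12, it gives 12 + 3 - 8 + 1 = 8, and Days 5 to 12 are 8 days. A length of 7 would add one day to every result.

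**Step 3: examples (assumed records, stop Day 12).**

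| Record | Formula | Within-period count left by the rule |
|---|---|---|
| Pain Days 0-7, later maximum blank | 12 + 8 - 8 + 1 = 13 | 8 |
| Pain Days 0-6, Day 7 blank, later maximum Grade 1 | 12 + 7 - 8 + 1 = 12 | 7 |
| Grade 1 on Days 5-7, later maximum blank | 12 + 3 - 8 + 1 = 8 | 3 |

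**Step 4: general size.** With stop day S, the formula exceeds the within-period count by S - 8 + 1 = S - 7 days. That is 1 day at S = 8, 5 days at S = 12 and 14 days at S = 21.

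**Step 5: the opposite gap.** In the first record, suppose the later maximum is Grade 1 and the stop date is missing. SAP 4.4.1.1.6 then returns Missing, not 8.

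**The case against.** **Which variable is affected.** A reader might infer that safety endpoints 2 and 3 are shortened, because they list number of days of occurrence. The documents do not support that. Those endpoints concern reactions from Day 0 through Day 7, and 4.4.1.1.5 derives that count without ongoing status. The rule reaches only ongoing status and the overall number of days. This part of the objection stands. SAP 5.3.1.5 does use the shorter term for a reaction continuing past the period, which shows that later days are meant to count somewhere.

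**The Day 7 cut-off is inferred.** The SAP never states the overall number of days for a reaction that is not ongoing. The within-period count is the only source left, but this is a deduction. That stands too, and the silence itself needs closing.

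**The stated reason for ignoring the flag.** It is tempting to say that this reason fails for pain, headache and other subjectively graded reactions because nothing is measured. That goes too far: 4.4.1.1.1 speaks of an intensity or a measurement, and a recorded grade can settle ongoing status just as a size does. The reason fails only when the record is absent.

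**Missing as a break.** SAP 4.4.1.1.4 treats a Missing day as interrupting a reaction, and the last daily intensity might mean the last available record. Both points weaken the Day 7 blank example. Neither touches the example with a blank later maximum.

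**Rarity.** Protocol 11.1, 11.2 and 13.2 have sites and data management clarify missing diary data. That should make such records less common, but it does not change what happens to those that remain.

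**Sub-threshold reactions.** Adult redness or swelling below 25 mm is below Grade 1 (Protocol Table 9.3), and fever starts at 38.0°C (Tables 9.4 and 9.5). Letting a flag or date override a missing measurement could count findings that do not qualify. This is correct, and the fix must respect it.

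**Conclusion.** The concern holds for one derived variable and the status that feeds it. When the last daily intensity or the later maximum is Missing, SAP 4.4.1.1.7 classes the reaction as not ongoing even with a complete stop date after Day 7. The overall number of days then falls back to the within-period count. The shortfall is the stop day minus 7, for example 5 days for stop Day 12.

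This rests on a solicited period of 8 days, on a literal reading of the all-other-cases sentence, and on the within-period count being the only fallback. The Day 7 blank case also assumes that the last daily intensity means Day 7.

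It does not follow that every late stop date is lost: when both intensities are at least Grade 1, the date is used. Nor are occurrence, Day 0-7 intensity, time to onset or the within-period days affected. The documents give no rate of missing diary entries, so the number of affected subjects cannot be estimated. In a descriptive study of about 60 subjects per group the effect is confined to the upper end of the duration summary. It is worth correcting because the short count gives no sign that data are missing and the remedy is cheap.

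**What to change.** Replace the closing sentence of SAP 4.4.1.1.7 with rules that separate a recorded None from a Missing value:

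1. Keep not ongoing when either recorded intensity is None. Also keep it when the later maximum is blank and there is neither an ongoing flag nor a stop date after Day 7.
2. For subjectively graded reactions, if exactly one of the two intensities is Missing, the other is at least Grade 1, and a complete stop date after Day 7 is recorded, class the reaction as ongoing and apply the 4.4.1.1.6 formula.
3. Set both ongoing status and the overall number of days to Missing in the remaining cases with a Missing intensity: measurable reactions (fever, redness, swelling), records with both intensities Missing, and records where only the flag points to continuation. Report how many there are.

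In 4.4.1.1.6, state what the overall number of days is for a reaction that is not ongoing, and give the solicited-period length as 8 days.

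The cost is a few SAP sentences and minor programming. The SAP already refers to both the flag and the stop date, so no new data are needed. The downside is that a few durations become longer or Missing.

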#### 4.4.1.2 Unsolicited Non-serious AEs

##### 4.4.1.2.1 Intensity

Intensity for unsolicited non-serious AEs will be derived according to the following classification: None, Grade 1, Grade 2, Grade 3, or Missing.

If the unsolicited non-serious AE is measurable and its PT is part of the list of solicited reactions, then the measurement will be derived based upon and following the same rule as the intensity scales defined in the protocol for that measurable injection site or systemic reaction.

Intensity for other unsolicited non-serious AEs will correspond to the value reported in the eCRF. The maximum intensity will correspond to the highest intensity for a unique term.

##### 4.4.1.2.2 Last Vaccination

The last vaccination before an unsolicited non-serious AE is derived from the visit numbers provided in the clinical database and will be calculated as follows:

- If an unsolicited non-serious AE has a non-missing visit number, the visit number will be used to determine the last vaccination before the unsolicited non-serious AE
- If the visit number is missing, then the start date of the unsolicited non-serious AE will be used to determine the last vaccination before the unsolicited non-serious AE

##### 4.4.1.2.3 Time to Onset

Time to onset will be derived from the start date of the unsolicited non-serious AE provided in the clinical database and the date of last vaccination:

start date of the unsolicited non-serious AE - date of previous vaccination

The time to onset will be considered as missing only if 1 or both of the dates are missing or partially missing.

Adverse events with a missing time to onset will be considered to have occurred just after the vaccination indicated by the visit number and will be included in tables. For subjects who received 2 doses, the worst-case scenario will be used for the post-any dose summary (i.e., the shorter time to onset [latency] period will be used if present for both doses or the available time to onset [latency] period will be used if present for either dose).

Note: Unsolicited non-serious AEs that occurred before vaccination (negative time to onset) will not be included in the analysis, but will be listed separately.

##### 4.4.1.2.4 Duration

Duration will be derived from the start and stop dates of the unsolicited non-serious AE provided in the clinical database:

stop date of unsolicited non-serious AE - start date of unsolicited non-serious AE + 1

The duration will be considered as missing only if 1 or both of the start and stop dates of the unsolicited non-serious AE is missing or partially missing. For subjects who received 2 doses, the worst-case scenario will be used for the post-any dose summary (i.e., the longer duration will be used if present for both doses or the available duration will be used if present for either dose).

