- Intensity of the event:
 - For measurable unsolicited non-serious AEs that are part of the list of solicited reactions, the size of the AE as well as the temperature for fever will be collected and analyzed based on the corresponding scale used for solicited reactions (see Table 9.1, Table 9.2, Table 9.3, Table 9.4, and Table 9.5)
 - Other unsolicited non-serious AEs will be classified according to the following intensity scale:
 - Grade 1: No interference with activity
 - Grade 2: Some interference with activity
 - Grade 3: Significant; prevents daily activity
- Action taken for each AE, if any (e.g., medication)

The action taken by the subject or subjects' parent(s)/guardian(s) to treat any **unsolicited AEs** will be classified in the eCRF using the following scale:

0: None

1: Medication (self-medication with an existing prescription or over-the-counter medication)

^a The stop date of all related AEs will be actively solicited. For other events, the Investigator will provide the stop date when it becomes available. Adverse events for which no stop date was obtained during the course of the study will be considered as ongoing at the end of the study.

- 2: Health care provider contact (no new medication prescribed)
- 3: Health care provider contact and prescription of a new medication (health care provider instructed subject to take a new medication, either an over-the-counter medication or one requiring a written prescription)

- Whether the AE led to discontinuation
- Whether the AE was related to vaccination (for unsolicited systemic AEs)

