#### 5.3.1.5 Start Date and Stop Date

No replacement of missing dates will be performed.

For instance:

- If the onset of an AE cannot be calculated due to a missing start date, then the onset will be considered as missing
- If the stop date of an unsolicited AE is missing, then the duration of that AE will be considered as missing
- If the stop date of a solicited reaction continuing after the solicited period is missing or incomplete, then the number of days of occurrence of that solicited event will be considered as missing

All missing and partially missing dates will be listed where appropriate.

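### Unsolicited AEs still ongoing at study end get no duration, so durations describe resolved events only, and the any-dose 'worst-case' rule can report the shorter, resolved event.

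*SAP*

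**What the plan says.** **Protocol 9.3.1.3.3**, in the footnote on start and stop dates, covers an AE for which "no stop date was obtained during the course of the study will be considered as ongoing at the end of the study". The same footnote says that stop dates of related AEs are actively sought, while for other events the investigator supplies the date if it becomes available.

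**SAP 4.4.1.2.4** computes duration as "stop date of unsolicited non-serious AE - start date of unsolicited non-serious AE + 1". It then states: "The duration will be considered as missing only if 1 or both of the start and stop dates" are missing or partially missing. For subjects given two doses, it describes the post-any-dose summary as worst-case: "the longer duration will be used if present for both doses or the available duration will be used if present for either dose".

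**SAP 5.3.1.5** confirms this: "No replacement of missing dates will be performed", and "If the stop date of an unsolicited AE is missing, then the duration of that AE will be considered as missing".

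**SAP 4.4.1.3.3** applies the same method to SAEs. By contrast, **SAP 4.4.1.1.7** derives an explicit ongoing status for solicited reactions. No equivalent exists for unsolicited AEs.

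Duration is listed in safety endpoints 1 and 4 (protocol 9.3.1.2, SAP 4.3.1.2). It is not listed in endpoint 5, which covers SAEs.

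**The concern.** The protocol gives a missing stop date a meaning: the event has not ended. The SAP handles the same event as one whose duration is unknown. Whether a duration is available then depends on the duration itself. The longer an event lasts, or the later in follow-up it starts, the more likely its duration is lost. What remains is a description of events that resolved.

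The any-dose rule adds a second fault. It is meant to carry forward the worse of two events, but a missing value cannot compete. A short resolved event is then chosen over a longer one that has not ended, which is the opposite of what the label promises.

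At stake is one descriptive attribute of unsolicited AEs, in a study whose objectives include describing safety.

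**Working it through.** The documents give no figure on this point, so there is none to reproduce. The check applies the written rules literally.

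**1. The chain of rules.** An ongoing AE has no stop date (protocol 9.3.1.3.3). With no stop date, the duration is missing (SAP 4.4.1.2.4 and 5.3.1.5). No date is substituted (SAP 5.3.1.5). So only events with complete start and stop dates contribute a duration.

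**2. The any-dose rule.** Inputs from the documents are the duration formula, the any-dose rule, and Visit 3 at 28 to 35 days after Visit 2. The event dates are assumed.
- Dose 1 event, days 2 to 4, resolved: 4 − 2 + 1 = 3 days.
- Dose 2 event, starting on day 5 after dose 2 and ongoing at Visit 3: stop date missing, so duration missing.
- Any-dose value under the SAP: the only available duration, 3 days.
- Minimum already observed for the dose 2 event: 28 − 5 + 1 = 24 days if Visit 3 is on day 28, or 35 − 5 + 1 = 31 days if it is on day 35.

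This result needs no distributional assumption.

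**3. Direction and possible size of the loss.** These inputs are assumptions, not from the documents: onset uniform over days 0 to 27, exponential durations with mean parameter m rounded up to whole days, last visit on day 28, and no stop date obtained later. An event starting on day s with duration d is ongoing if s + d − 1 > 28, that is, d > 29 − s. Hence

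share ongoing = (1/28) × Σ exp(−k/m), for k = 2 to 29.

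The shares follow from the formula. The resolved-only medians come from simulating the same model.

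| m (days) | Share ongoing | Median, all events | Median, resolved only |
|---|---|---|---|
| 5 | 13% | 4 | 3 |
| 10 | 29% | 7 | 5 |
| 20 | 50% | 14 | 7 |
| 40 | 69% | 28 | 8 |

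The direction is always short. The size depends on how long-lasting the events are. The assumption of no later stop dates makes these figures too pessimistic for related AEs.

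**The case against.** Several points on the other side stand and limit the finding.

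- **Stop dates of related AEs are pursued.** The protocol footnote says they are actively sought. Protocol 9.3.1.3.6 follows likely-related AEs that persist at study end until they disappear or stabilize, and protocol 5.1.4 follows related events and those that led to discontinuation. A reader might infer that the longest events disappear regardless of cause, but the documents do not support that.
- **No summary statistic for duration is specified.** SAP Table 5.1 gives only counts, percentages and numbers of events for safety, and the SAP 5.1.3.1 text on unsolicited AEs names nature and relationship. A reader might be tempted to say that the plan understates a mean duration by some number of days. The SAP specifies no such mean, so no such number can be given.
- **Ongoing events are not necessarily invisible.** SAP 5.3.1.5 provides for listing missing and partial dates. Incidence is untouched, because its denominator is vaccinated subjects (SAP 5.1.3.1).
- **SAEs.** Endpoint 5 does not include duration, so applying the rule to SAEs affects no stated endpoint.
- **Scope.** The any-dose fault concerns only two-dose children within Groups 1 and 2, at most about 60 + 60 = 120 planned subjects. A dose 1 event in such a child can be followed for about 56 to 70 days (28 + 28 to 35 + 35), so the realistic case is a resolved event after dose 1 and an ongoing one after dose 2. Endpoint 1 events begin within 20 minutes of vaccination, so late onset cannot cause loss there. Only long duration can.

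None of this changes the derivation: an event defined as ongoing still contributes no duration, and the worst-case rule can still select the milder case.

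**Conclusion.** The concern holds in limited form. Under the written rules, duration in endpoints 1 and 4 describes resolved unsolicited AEs only and is biased short. The loss falls mainly on unrelated AEs and on related AEs unresolved at lock. The any-dose rule can report 3 days where an ongoing event has already lasted at least 24 to 31 days.

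The direction of the bias follows from the text. Its overall size cannot be stated, because it depends on the mix of events. The 13% to 69% range above is an illustration resting on assumed onset and duration patterns.

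A reader might also infer that an ongoing event should always outrank a resolved one. That goes too far. An event that began on the day of Visit 3 has an observed minimum of 1 day and should not displace a resolved 25-day event.

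This is a modest descriptive fault that should be corrected. It does not affect AE counts, percentages or the immunogenicity results.

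**What to change.** In SAP 4.4.1.2.4 and 5.3.1.5:

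1. For an unsolicited AE with a known start date and no stop date that is ongoing at the last contact, report 'ongoing at end of study' as a separate duration category. Show the observed time, last visit or contact date − start date + 1, as a minimum ('at least x days').
2. Keep duration as missing where the event is not known to be ongoing at the last contact, for example after loss to follow-up. Time to a later termination date could then exceed the true duration.
3. In the any-dose rule, let the ongoing event take precedence when its observed minimum exceeds the resolved duration. Flag every subject with an ongoing event, whichever value is used.
4. If SAE duration is reported, apply the same derivation through 4.4.1.3.3.

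The cost is SAP wording and one table category. Start dates, visit dates and termination dates are already collected, and SAP 4.4.4.2 already uses the last two. The documents do not show whether the eCRF has an ongoing field for unsolicited AEs. If it does not, status would be taken from the diary and interim-history review at the last visit. No change in trial conduct is needed.
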